5. ANALYSIS POPULATIONS AND APPROACHES TO ANALYSIS

5.1 FULL ANALYSIS SET

The full analysis set (FAS) is defined as all randomized patients who received at least one dose of study treatment. Patients in this population will be analyzed according to the treatment arm to which they were assigned at randomization. The FAS will serve as the population for the analyses of efficacy, in keeping with the intent-to-treat (ITT) principle. Analyses of efficacy will provide an indication of potential benefit in the exploration to determine the recommended dose of pacritinib for further clinical studies.

5.2 SAFETY POPULATION

The safety population is defined as all randomized patients who received at least one dose of study treatment.

All safety analyses will be performed using the safety population, and patients in this population will be analyzed according to the treatment actually received. Treatment actually received will be

determined by the treatment initially taken. Safety analyses will provide an indication of potential risk in the exploration to determine the recommended dose of pacritinib for further clinical studies.

6. GENERAL STATISTICAL CONSIDERATIONS

6.1 DATA ANALYSIS CONVENTIONS

All data analysis will be performed by CTI or designee after the study is completed and the database has been locked and released. Statistical programming and analyses will be performed using SAS® version 9.4. Outputs will be provided in both RTF and PDF for tables, listings and figures using landscape orientation. Applicable study data will be listed at minimum by subject, treatment arm, and visit (as applicable) based on the analysis population as specified in this plan.

Summaries for continuous and ordinal variables will include the number of observations (n), arithmetic mean, standard deviation (SD), minimum, first quartile (Q1), median, third quartile (Q3), and maximum. Summaries of discrete variables will include frequency counts and percentages.

6.2 MULTIPLICITY

No formal statistical hypothesis testing will be performed, thus no multiplicity adjustment is needed.

7. DISPOSITION AND ENROLLMENT

Patient disposition will be presented as number and percentages of patients who were screened, randomized, completed the study, and discontinued the study. A completed patient will be one who has not been discontinued or withdrew consent from the study. Disposition will be summarized by treatment arm and for all study patients.

The number and percentage of patients prematurely discontinued from the study and the reasons for study discontinuation will be summarized for all randomized patients. The reasons for study termination include: withdrawal by patient, lost to follow-up, death, study termination by sponsor, physician decision and other reasons. In addition, the number of patients who discontinued treatment as well as the reasons for treatment discontinuation (adverse event, death, lost to follow-up, physician decision, study terminated by Sponsor, withdrawal by patient and other reasons) will be presented by treatment arm.

Study enrollment by country and region will be presented by treatment arm.

8. DEMOGRAPHICS, BASELINE CHARACTERISTICS, AND MEDICAL HISTORY

The demographic and baseline characteristics will be analyzed with the following variables in all randomized patients.

8.1 DEMOGRAPHIC VARIABLES

Age, age category (< 65 years vs. \geq 65 years), gender (female vs. male), race (American Indian or Alaska Native vs. Asian vs. Black or African American vs. Native Hawaiian or Other Pacific Islander vs. White vs. Other vs. Multiple), ethnicity (Hispanic or Latino vs. Non-Hispanic or Latino), height, weight, body mass index, and ECOG performance status (0 vs. 1 vs. 2),.

8.2 BASELINE DISEASE CHARACTERISTIC VARIABLES

Spleen length by physical exam, baseline platelet count and category (\leq 50,000/ μ L vs. $>$ 50,000/ μ L to \leq 100,000/ μ L vs. $>$ 100,000/ μ L), baseline hemoglobin and category (< 100 g/L vs. \geq 100 g/L), peripheral blasts percentage and category (< 1% vs. \geq 1%), white blood cell count and category (\leq 25x10 9 /L vs. $>$ 25x10 9 /L), current MF diagnosis (PMF vs. PPV MF vs. PET MF), time since current MF diagnosis, gene mutation status (JAK2V617F vs. other JAK2 vs. MPL vs. CALR vs. Triple Negative vs. Other vs. None), abnormal cytogenetics (Yes vs. No), unfavorable karyotype (Yes vs. No), current DIPSS score (1 vs. 2 vs. 3 vs. 4 vs. 5 vs. 6), DIPSS plus score (1 vs. 2 vs. 3 vs. 4 vs. 5 vs. 6), transfusion history (within 90 days prior to (Informed Consent date through the treatment start date + 1)), red blood cell (RBC) transfusion dependence as defined by the Gale criteria (Gale et al. 2011; Table 1), and platelet transfusion dependence (Table 2).

Table 1 – Definitions of Red Blood Cell Transfusion Dependence and Independence

	RBC Transfusions
RBC transfusion dependence	\geq 2 units/month
RBC transfusion independence	None
Reduced RBC transfusion dependence	50% decrease
Gale et al. 2011	

Table 2 – Definitions of Platelet Transfusion Dependence and Independence

	Platelet Transfusions
Platelet transfusion dependence	Any episode of platelet transfusion during the past month
Platelet transfusion independence	No platelet transfusion during the past month

8.3 PRIOR THERAPY AND CONCOMITANT MEDICATIONS

Prior therapy is any therapy or medication taken prior to informed consent. Prior therapy includes both prior MF and non-MF therapies. Both will be summarized for all enrolled patients by treatment and overall.

A medication will be considered a concomitant medication if it was taken by the patient at any time on study (on or after the first day of treatment and within 30 days after the last dose of study drug). The following will also be considered concomitant medications:

- Medications missing both start and stop dates.
- Medications having a start date prior to the last dose of study drug and missing the stop date.

Concomitant medications will be summarized by ATC class and preferred term in each treatment arm. Prior MF and non-MF therapies or medications will be summarized by Anatomic Therapeutic Chemical (ATC) class and preferred term using WHO Drug Dictionary version 01, March 2013.

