¹ Screening procedures must be completed between Days -35 and -7, before treatment initiation, with the exception of the screening (baseline) MRI or CT scan, which must be parformed between Days -10 and -4								
² Day 1 assessments are required to be performed prior to initiation of study treatment and can be performed up to 24 hours prior to initiation of study treatment. At the baseline visit, all patients will be provided with a prescription (and instructions to fill that prescription) for loperamide (Imodium) or a similarly effective antidiarrheal drug. Patients will be instructed to start taking the prescribed loperamide or other antidiarrheal drug per package and physician instructions as soon as they notice any change in frequency or consistency of bowel movements after starting study treatment.								
³ The study visit at week 4 has a scheduling window of ±3 days; however, all procedures other than MRI or CT should be performed on the same day's visit within ±24 hours. ⁴ The study visits at weeks 12 and 24 have a scheduling window of ±7 days; however, all procedures other than MRI or CT should be performed on the same day's visit within ±24 hours.								

Table 1. PAC203 Study Assessments Calendar²⁰

- ⁵ The End of Treatment visit is scheduled within 7 days after terminating study treatment. A final visit to assess events is scheduled 30 ±3 days after the last dose of study treatment. If treatment ends at a regularly scheduled visit, these procedures may be performed at that time.
- ⁶ Informed consent must be obtained before any study-specific washout. This may require 2 weeks (A 2-week washout will be required for anticoagulation agents, antiplatelet agents (except aspirin doses of ≤ 100 mg/day), strong CYP3A4 inhibitors, strong CYP450 inducers, and QTc prolonging agents) or 28 days if patient was taking any experimental therapies. Patients not requiring washout may sign the Informed Consent Form at any time prior to screening procedures.
- ⁷ Vital signs include blood pressure, pulse, respiratory rate, temperature, and body weight.
- ⁸ Height should be measured only at baseline. Spleen size assessed by physical examination as the distance below the LCM at the midclavicular line.

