6.6 Concomitant and Excluded Therapies

Ruxolitinib should not be administered concurrently with pacritinib at any time. Although there is no washout period required for ruxolitinib prior to the start of dosing with pacritinib, it should be understood that because of the difference in half-life between ruxolitinib (3 hours Jakafi package insert) and pacritinib (approximately 40 hours), there will be a period of 10 to 14 days following the discontinuation of ruxolitinib and the start of dosing with pacritinib, during which pacritinib has not yet reached steady state and during which patients may be at increased risk of ruxolitinib withdrawal, particularly after high doses of ruxolitinib (eg, more than 10 mg BID or 20 mg QD). For this reason, patients who are on more than 10 mg BID (or 20 mg QD) of ruxolitinib at the time of consent for this study must taper the ruxolitinib dose down to 10 mg BID or lower and remain stable on the reduced dose for at least 2 weeks prior to starting pacritinib. Tapering should be done per institutional practice and may be done with concurrent addition of prednisone during the screening period. In addition to any steroids used during the screening period, the protocol permits short-term use (up to 14 days) of corticosteroids and/or hydroxyurea as prophylaxis or treatment of symptomatic ruxolitinib withdrawal during the first month of treatment with pacritinib.

Supportive care therapies, except when prohibited by any of the below provisions, are permitted, including the use of low-dose aspirin. Corticosteroids (up to 20 mg/day of prednisone or equivalent) and/or hydroxyurea may be used for up to 2 weeks during the first month of treatment with pacritinib to control symptoms of ruxolitinib withdrawal if they occur. Treatments for MF that might be considered supportive care are only allowable with medical monitor approval prior to administration.

The following therapies and procedures are prohibited throughout the study:

- Chemotherapy, interferon, or other treatment for MF, with the exception of up to 2 weeks of corticosteroids (up to 20 mg/day prednisone or equivalent) and/or 2 weeks of hydroxyurea as needed to reduce the risk of or treat the symptoms of ruxolitinib withdrawal
- Antiplatelet or anticoagulation agents, with the exception of $\leq 100 \text{ mg/day}$ of aspirin
- Growth factor therapies, including erythropoietin and thrombopoietin

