8.4 Prior Ruxolitinib Experience

The experience of patients with prior ruxolitinib therapy will be summarized as well. Descriptive statistics for the following characteristics will be presented by treatment arm and overall: prior ruxolitinib treatment experience, ruxolitinib treatment duration, time since last ruxolitinib treatment, most recent ruxolitinib total daily dose and dose category (< 10 mg/day vs. \geq 10 mg/day), highest ruxolitinib total daily dose, the lowest hemoglobin at start of and on ruxolitinib therapy, RBC transfusion requirements prior to and at the end of ruxolitinib therapy, the lowest platelet count at start of and on ruxolitinib therapy, and adverse events experienced, patients with reduction in spleen length and volume, and patients with clinically meaningful reduction in symptoms while on ruxolitinib therapy. The reasons for discontinuing ruxolitinib therapy will also be summarized.

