17.5 Partial or Missing Concomitant Medication and Supplemental Procedure Dates

For concomitant medication, when missing the start date information the following imputation will be applied:

Derive data only with the missing day of the month:

- First day of the month that the CM occurred if this is after the date of the start of first treatment.
- One day after the first treatment if this is the same month that the CM occurred.
- The 15th of the month and year if the CM month and year are before the month and year of the first treatment.

Derive data if both day and month are missing:

- January 1 of the year of onset, as long as this is after the first study treatment.
- One day after the first study treatment if this is the same year that the AE occurred.
- July 15th of the year if the CM year is before the year of the first study treatment.

When missing the end date information the following imputation will be applied:

Derive data only with the missing day of the month:

- Set as the last day of the month

Derive data with both missing day and month:

- set as December 31th

All missing and partial dates will be presented “as is” in listings

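### SAP 8.3 leaves medications taken only between consent and first dose out of both summary tables, and SAP 17.5 can impute a partial ruxolitinib stop date on or after the first pacritinib dose

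*SAP*

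**What the plan says.** SAP 8.3 defines two categories. For the first, "Prior therapy is any therapy or medication taken prior to informed consent". The second, concomitant, covers anything taken "on or after the first day of treatment and within 30 days after the last dose of study drug". Two further kinds of record are also counted as concomitant: "Medications missing both start and stop dates" and "Medications having a start date prior to the last dose of study drug and missing the stop date". Both concern missing dates; neither deals with the interval between consent and Day 1.

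Protocol 6.6 expects medication in that interval. Patients on higher ruxolitinib doses must taper before starting pacritinib, and the taper "may be done with concurrent addition of prednisone during the screening period". The same section requires no ruxolitinib washout and bars ruxolitinib given together with pacritinib. Protocol Table 1 collects concomitant medications at screening and at baseline. Its first footnote sets the length of the interval: "Screening procedures must be completed between Days -35 and -7, before treatment initiation".

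For an end date with the day missing, SAP 17.5 gives the rule "Set as the last day of the month". With day and month both missing, the date becomes 31 December. SAP 8.4 summarises, among other items, "time since last ruxolitinib treatment".

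**The concern.** The two definitions in SAP 8.3 do not meet. One ends at consent and the other begins at first dose, so a medication confined to the interval belongs to neither. The medications most likely to sit there are those used to manage the move from ruxolitinib to pacritinib, and a reader of the tables could not see how often they were used or whether use was balanced across arms.

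The end-date rule has a related weakness. The start-date rules in SAP 17.5 refer to first treatment; its end-date rules refer to nothing. Because ruxolitinib can run up to the start of pacritinib, its true stop may lie shortly before first dose, and moving a partial date to the end of the month or year can carry it past first dose. The record would then look like prohibited concurrent use. It would also distort one of the summaries of prior ruxolitinib treatment, which every patient in this trial must have had.

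**Working it through.** The plan states no figure on this point, so the check applies its rules literally to dates. All example dates are illustrative.

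**1. The gap in SAP 8.3**

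Take consent on 1 May, a steroid from 8 to 29 May, and first dose on 5 June (35 days after consent).
- Prior? Taken before 1 May: no.
- Concomitant? Taken on or after 5 June: no.
- Missing-date exceptions? Both dates are known: not applicable.

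The steroid is in neither table. Had it continued to 5 June, or had its stop date been missing, it would have been concomitant. The gap is therefore confined to fully dated medications that lie wholly inside the interval.

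**2. The end-date rule in SAP 17.5, one patient**

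Take ruxolitinib stopped on 11 June and first dose on 12 June.

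| Stop date recorded | Date used | First dose minus stop | Tables |
|---|---|---|---|
| Complete | 11 June | +1 day | prior |
| Day missing | 30 June | 12 − 30 = −18 days | prior and concomitant |
| Day and month missing | 31 December | −202 days | prior and concomitant |

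The record stays in the prior table, because the drug was also taken before consent, and is added to the concomitant table.

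**3. How often the imputed stop falls on or after first dose**

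Let L be the days from the true stop to first dose, and let first dose be equally likely on each of the 365 days of a year.
- Day missing: the imputed stop reaches first dose only if the two dates share a calendar month, that is, if first dose falls later than day L of its month. For L up to 28, every month contributes its length minus L, so the share is (365 − 12L)/365.
- Day and month missing: the two dates must share a calendar year, so the share is (365 − L)/365.

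| L (days) | Day missing | Day and month missing |
|---|---|---|
| 1 | 353/365 = 96.7% | 364/365 = 99.7% |
| 7 | 281/365 = 77.0% | 358/365 = 98.1% |
| 14 | 197/365 = 54.0% | 351/365 = 96.2% |
| 28 | 29/365 = 7.9% | 337/365 = 92.3% |
| 35 | 0% | 330/365 = 90.4% |
| 60 | 0% | 305/365 = 83.6% |

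Averaged over L = 1 to 7 (mean L = 4):
- Day missing: (365 − 48)/365 = 86.8%. Counting first dose and imputed stop as whole days, the mean false overlap among affected records is 13.8 days.
- Day and month missing: 361/365 = 98.9%, with a mean overlap of 181 days.

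Averaged over L = 1 to 30, the day-missing share is 5,373/10,950 = 49.1%. The count here is month by month, because the short formula stops at L = 28.

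These are shares of records that already have a partial stop date. The documents do not say how many there will be.

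**The case against.** Several points on the other side carry weight.

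**Scope of SAP 17.5.** Its text opens by naming concomitant medication, and ruxolitinib stopped before Day 1 is prior therapy. The statement that the rule handles prior medications too is in the SAP's table of modifications. Nor do the documents show whether the SAP 8.4 variables come from medication records subject to 17.5 or from a separate ruxolitinib history form. This stands: the ruxolitinib half is conditional on the rule being applied to those records.

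**Plausibility of the missing dates.** A patient who stops ruxolitinib in the week before pacritinib has normally consented and is being seen at the site, so a missing day is unlikely and a missing month more so. Partial dates are more plausible for stops well before consent, where the missing-day rule does no harm. This also stands, and it is why the percentages cannot be read as shares of patients.

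**Nothing is lost from the database.** SAP 6.1 provides by-subject listings and SAP 17.5 shows partial dates there unaltered. That is correct. The defect is in the summaries.

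**Latest-date imputation is a recognised conservative choice**, in line with SAP 8.3 counting records without a stop date as concomitant. Capping every uncertain stop at the day before first dose would assume compliance and could hide genuine overlap. This is right, and it limits the remedy.

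A reader might go further and infer that unreported screening steroids bias the baseline against which spleen volume and symptom reductions are measured. The documents do not support that. SAP 10.1 and 10.2 compute baseline and percent reduction without the medication category, and reclassifying a drug changes no value. Neither document says that such steroids alter spleen volume or symptom score. SAP section 5 defines only the full analysis set and the safety population, and neither excludes patients for prohibited medication.

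**Conclusion.** The gap in SAP 8.3 holds as a matter of definition: a fully dated medication confined to the interval from consent to first dose is in no summary table, and the protocol permits at least one such use.

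The SAP 17.5 problem holds conditionally. It needs a partial stop date, application of the rule to prior medications, and a true stop in the same calendar month (day missing) or year (day and month missing) as first dose. It would be wrong to read it as affecting every partial ruxolitinib stop date: with only the day missing, the share falls from 96.7% at one day to nil at 35 days. The calculation also assumes first-dose dates spread evenly over the year.

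The consequences are confined to the medication tables and the prior-ruxolitinib summary. No efficacy or primary safety result depends on either rule. It is worth correcting because the rules as written give incomplete tables and could show prohibited use that did not happen.

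**What to change.** In SAP 8.3, define prior as taken before the first dose of pacritinib, or add a third category running from consent to first dose, so that every recorded medication falls in at least one table.

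In SAP 17.5, state that the section applies to prior medications. Limit an imputed end date to the day before first dose only where the record shows that the drug had stopped before treatment, for example because it was entered as prior therapy or as not ongoing at baseline. In all other cases keep the latest-date imputation, so that real overlap remains visible.

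The cost is about two sentences in the SAP and the matching programming. Data collection and trial conduct do not change.

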8.4 Prior Ruxolitinib Experience

The experience of patients with prior ruxolitinib therapy will be summarized as well. Descriptive statistics for the following characteristics will be presented by treatment arm and overall: prior ruxolitinib treatment experience, ruxolitinib treatment duration, time since last ruxolitinib treatment, most recent ruxolitinib total daily dose and dose category (< 10 mg/day vs. \geq 10 mg/day), highest ruxolitinib total daily dose, the lowest hemoglobin at start of and on ruxolitinib therapy, RBC transfusion requirements prior to and at the end of ruxolitinib therapy, the lowest platelet count at start of and on ruxolitinib therapy, and adverse events experienced, patients with reduction in spleen length and volume, and patients with clinically meaningful reduction in symptoms while on ruxolitinib therapy. The reasons for discontinuing ruxolitinib therapy will also be summarized.

8.5 Medical History

Medical history is any disease that occurred prior to informed consent. Medical history will be summarized by frequency distribution (n and %) of system organ class and preferred term by MedDRA dictionary version 16.0 for all enrolled patients.

9. EXPOSURE TO STUDY TREATMENT

Exposure to study treatment will be evaluated by the duration of treatment, cumulative dose, actual dose intensity, and relative dose intensity in the safety population.

Duration of treatment (weeks): is defined as the duration from first day of study treatment to the last day of study treatment, i.e.,

$$\frac{(\text{Date of last dose of study treatment} - \text{date of first dose of study treatment} + 1)}{7}$$

Descriptive statistics will be provided for duration of treatment by treatment arm.

Cumulative dose (mg): is defined as the sum of all doses of study treatment taken and descriptive statistics will be provided by treatment arm. The counts and percentages of patients with any dose modifications will be provided by treatment arm. Reasons for dose modifications will also be summarized.

Actual dose intensity (ADI, mg/day) = (total dose taken in mg) ÷ (duration of treatment in days) and descriptive statistics will be provided by treatment arm.

Relative dose intensity (RDI, %) = (ADI) ÷ (planned daily dose) * 100. The planned pacritinib dose is 100, 200, and 400 mg/day in the pacritinib 100 mg QD, 100 mg BID, and 200 mg BID arms, respectively. Descriptive statistics will be provided by treatment arm.

Study drug modification categories will be defined for drug holds and drug reduction. Drug holds will be identified by those records with dose entered as 0mg. Drug reduced will be identified by evaluating the subject's initial dose and determining if a reduction occurred at any time during the treatment period.

Finally, reasons for drug modifications will be presented by treatment arm.

